7.18 Pharmacokinetic Analyses

The serum levels of VHH will be determined before, 2 hours, and 24 hours after the first dose; Day 8, Day 28, and Day 29. If serum levels of VHH are detected, PK results will be summarized. Stool samples will be collected at baseline and on Days 2, 8, 28 and 29, supernatant collected, and the supernatant stored in a stool bank.

7.19 Potential Toxicities

The potential toxicities of LMN-101 are primarily related to the effects associated with monoclonal antibodies (mAbs) in general. As with all drugs and biologics, there is the potential for individual allergic reactions. Considerable human experience has been accumulated with mAb therapy. The adverse effects of treatment with mAbs are diverse and appear to be dependent on the species of origin (murine versus human) and the antigenicity of the antibody. To date, there is no other reported clinical experience with another mAb against campylobacter.

Potential toxicities that may exist with LMN-101 include the formation of antibodies against LMN-101. Since LMN-101 is a protein macromolecule administered orally, systemic absorption is not anticipated so the risk of formation of anti-drug antibodies is low. Please see the Investigator's Brochure for additional information.

Since LMN-101 is a subunit of an antibody and does not contain an Fc domain, there is not a possibility of Fc binding. Since LMN-101 is directed against a bacterial antigen that does not cross-react with human tissue, there is no anticipated non-specific binding to human tissue.

While there is theoretically a remote possibility of a potential effect on the normal gut microbiome, antibodies against the target antigen, FlaA of campylobacter flagellin do not cross react with normal flora of the gut microbiome.

8 ADVERSE EVENTS (AEs)

An AE is the development of an undesirable medical condition or the deterioration of a preexisting medical condition following or during exposure to a pharmaceutical product, whether considered caused by the product or not. In clinical studies, an AE can include an undesirable medical condition occurring at any time, including baseline or washout periods, even if no study treatment has been administered.

All AEs that occur after any subject has been enrolled, before treatment, during treatment, or within days following the cessation of treatment, whether they are related to the study or not, must be recorded on forms provided by Lumen Bioscience or its representative. Lumen Bioscience and the investigators must abide by the Australian Health Ethics Committee statement "Safety monitoring and reporting in clinical trials involving therapeutic goods." http://health.act.gov.au/sites/default/files//REGO/28.%20AHEC%20Position%20Statement%20 -%20Safety%20Reporting%20-%20November%202016.pdf

8.1 Serious Adverse Events (SAE)

A SAE is an AE occurring during any study phase (i.e., baseline, treatment, or follow-up), and at any dose of the investigational product or placebo, that fulfills one or more of the following criteria:

- Results in death
- It is immediately life-threatening
- It requires inpatient hospitalization or prolongation of existing hospitalization
- It results in persistent or significant disability or incapacity
- Results in a congenital abnormality or birth defect
- It is an important medical event that may jeopardize the subject or may require medical intervention to prevent one of the outcomes listed above.

Important medical events that may not result in death, be life-threatening, or require hospitalization may be considered a serious adverse experience when, based upon appropriate medical judgment, they may jeopardize the subject and may require medical or surgical intervention to prevent one of the outcomes listed above.

All SAEs that occur after any subject has been enrolled, before treatment, during treatment, or within 28 days following the cessation of treatment, whether they are related to the study or not, must be recorded on forms provided by Lumen Bioscience or its representative.

Any serious or unexpected AEs must be reported to Lumen Bioscience or its representative, including death or life-threatening events, disabling or incapacitating conditions, or any event that requires hospitalization. SAEs occurring during the duration of the study or within four weeks of the subject's last treatment must be reported within 24 hours to Lumen Bioscience or its representative, even if the event appears unrelated to the treatment. See the Study Manual for specific instructions for reporting SAEs.

Lumen Bioscience Medical Monitor 24-hour contact information: [name] Chief Medical Officer Lumen Bioscience, Inc. [name] [contact] [contact] business [contact] mobile

Lumen Bioscience back-up Medical Monitor 24-hour contact information: [name] Cascadia Drug Development Group [name] [contact] [contact] mobile

Both Lumen Bioscience and Investigators have the right to terminate this study at any time, and to arrange an appropriately agreed upon schedule for termination, if necessary. This information will be provided to each subject or legally authorized representative during the informed consent process.

SAEs will be reported to the FDA and/or relevant national regulatory authorities within the required time frames to meet the safety reporting requirements, i.e., a 7-day IND safety report for unexpected fatal or life-threatening suspected adverse reactions, an IND safety report for 15-day reports, or a follow-up IND safety report for follow-up information.

8.2 Relationship to Treatment

An Investigator who is qualified in medicine must make the determination of relationship to the treatment for each AE (Unrelated, Possibly Related or Probably Related). The Investigator should decide whether, in his or her medical judgment, there is a reasonable possibility that the event may have been caused by the treatment. If no valid reason exists for suggesting a relationship, then the AE should be classified as "unrelated." If there is any valid reason, even if undetermined, for suspecting a possible cause-and-effect relationship between the treatment and the occurrence of the AE, then the AE should be considered "related."

If the relationship between the AE/SAE and the treatment is determined to be "possible" or "probable" the event will be considered to be related to the treatment for the purposes of expedited regulatory reporting.

8.3 Recording Adverse Events

AEs spontaneously reported by the subject and/or in response to an open question from the study personnel or revealed by observation will be recorded during the study at the investigational site. Clinically significant changes in laboratory values, blood pressure, and pulse need not be reported as AEs since they will be captured in those data listings. However, abnormal values that constitute an SAE or lead to discontinuation of administration of treatment must be reported and recorded as an AE. Information about AEs will be collected from the signing of the consent form until the end of the study. SAE information will be collected from signing of the consent form until 28 days following the last dose of treatment. The AE term should be reported in standard medical terminology when possible. For each AE, the Investigator will evaluate and report the onset (date and time), resolution (date and time), intensity, causality, action taken, serious outcome (if applicable), and whether or not it caused the subject to discontinue the study.

Intensity will be assessed according to the CTCAE Version 5.0. A pdf of these criteria is attached as Appendix A.

It is important to distinguish between serious and severe AEs. Severity is a measure of intensity whereas seriousness is defined by the criteria under the Section above entitled Serious Adverse Event. An AE of severe intensity may not be considered serious.

Should a pregnancy occur, it must be reported and recorded in the source documents and Medical History form in the CRF. Pregnancy is not regarded as an AE unless there is a suspicion that an investigational product may have interfered with the effectiveness of a contraceptive medication.

The outcome of all pregnancies (spontaneous miscarriage, elective termination, normal birth or congenital abnormality) must be followed up and documented even if the subject was discontinued from the study.

All reports of congenital abnormalities/birth defects are SAEs. Spontaneous miscarriages should also be reported and handled as SAEs. Elective abortions without complications should not be handled as AEs.

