4.3 Safety Criteria for Stopping Dosing

Advancing to the next dose cohort will be done after review of safety data by the PI and the Sponsor's Medical Monitor, both of whom are unblinded as to treatment assignment in Part A and blinded as to treatment assignment in Part B. If a dose is safe, then the next dose cohort will be enrolled. Criteria that would result in a pause in active dosing and further investigation by the study team include if any subject experiences a SAE deemed related to the study drug; if two or more subjects experience the same grade 3 or higher AE; if accumulation of SAEs and/or AEs collectively raises a safety concern in the opinion of the investigator, research monitor, or study sponsor; or if any subject experiences an adverse event of special interest (AESI).

If a subject develops a significant allergic reaction or anaphylaxis following study drug administration, the study drug will be immediately discontinued for that subject and no further doses given. The PI should contact the Sponsor's Medical Monitor to determine whether to discontinue study treatment for a given subject. Regardless of communication with the Sponsor, the PI is authorized to discontinue the study drug at any time if it is in the best interest of the safety of the subject. Treatment may also be discontinued at the request of the subject.

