7.17 Safety Analysis

The analysis of safety will include all subjects who received study drug. Safety will be evaluated from reported AEs, physical examination findings, vital signs, and clinical laboratory values as described below:

- The incidence and number of all reported AEs and treatment-related AEs will be tabulated by treatment group. AEs will be classified by Organ System Classification.
- AEs and SAEs will be summarized by organ system classification, severity, and relationship to study drug. In the event of multiple occurrences of the same AE with the same preferred term in the same subject, the AE will be reported as the number of AEs and with the AE counted only once. The incidence of AEs will be tabulated by Organ System Class and treatment group.
- AEs indicative of secondary infection will also be compared between treatment groups.

• SAEs will be presented as listings by treatment group. The event, start and stop dates and times, relationship to study drug, severity, and outcome will be presented. Outcomes attributed to SAEs will be tabulated separately by treatment group.

Tolerability will be assessed by the proportion of participants completing study drug and remaining on study and free from possibly drug-related and dose-limiting SAEs to the end of follow-up.

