### **12.1 Adverse Events**

#### **12.1.1 Endpoints**

- AE
- SAE
- TEAE

AEs and SAEs are defined in the study protocol. TEAEs are defined as adverse events that occurred or worsened following the first administration of study medication.

All AEs will be coded using MedDRA. AE summaries will be restricted to TEAEs only.

Summary tables will include the number of participants (%) experiencing an event and the number of events. Participants will be counted only once at each SOC and PT level of summary.

The TEAE summaries will include:

- Overall Summary of TEAEs
  - Number of TEAEs
  - Number of TEAEs with Toxicity  $\geq$  Grade 3
  - Number of Serious TEAEs
  - Number of Study Drug Related TEAEs (Drug Related: A Possibly or Probably related TEAE)
  - Number of TEAEs leading to study withdrawal
- TEAE and SAE summary by SOC and PT
  - TEAEs
  - Treatment Emergent SAEs
  - TEAE by relationship to Study Drug
  - TEAE summary by Toxicity Grade

All AEs will be listed and will include verbatim term, PT, SOC, treatment group, relationship to study drug, toxicity grade, seriousness, reason for serious event, outcome, and action taken with regards to the study drug and AE. Separate listings will be created for SAEs and events leading to study drug withdrawal.

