**Programming Note:**

- Include all ATCs and all PTERMs.

Sponsor: Lumen Bioscience, Inc.  
 Protocol: CAM01

Database Lock: yyyy-mm-dd

Table 14.3.3.1 Overall Summary of Treatment-Emergent Adverse Events (Safety Analysis Set)

	Part A:		Part B:		LMN-101 Overall (N=xx) n (%) m	Placebo (N=xx) n (%) m	Overall (N=xx) n (%) m
	LMN-101 3000 mg (N=xx)	LMN-101 300 mg (N=xx)	LMN-101 100 mg (N=xx)	LMN-101 3000 mg (N=xx)			
	n (%) m	n (%) m	n (%) m	n (%) m			
Number of subjects reporting at least:							
One TEAE	xx (xx.x%) xx	xx (xx.x%) xx	xx (xx.x%) xx	xx (xx.x%) xx	xx (xx.x%) xx	xx (xx.x%) xx	xx (xx.x%) xx
One Grade 3 or Higher TEAE	xx (xx.x%) xx	xx (xx.x%) xx	xx (xx.x%) xx	xx (xx.x%) xx	xx (xx.x%) xx	xx (xx.x%) xx	xx (xx.x%) xx
One Serious TEAE	xx (xx.x%) xx	xx (xx.x%) xx	xx (xx.x%) xx	xx (xx.x%) xx	xx (xx.x%) xx	xx (xx.x%) xx	xx (xx.x%) xx
One Drug Related TEAE	xx (xx.x%) xx	xx (xx.x%) xx	xx (xx.x%) xx	xx (xx.x%) xx	xx (xx.x%) xx	xx (xx.x%) xx	xx (xx.x%) xx
One TEAEs Leading to Drug Withdrawal	xx (xx.x%) xx	xx (xx.x%) xx	xx (xx.x%) xx	xx (xx.x%) xx	xx (xx.x%) xx	xx (xx.x%) xx	xx (xx.x%) xx

Note: A treatment-emergent adverse event (TEAE) is defined as an adverse event that occurred or worsened following the first administration of study drug. If a subject has multiple occurrences of a TEAE, the subject is presented only once in the Subject count (n) column. Occurrences are counted each time in the mentions/Occurrence (m) column.

Related TEAE = A Possibly Related or Related TEAE.  
 MedDRA Version xx.x

Sponsor: Lumen Bioscience, Inc.  
 Protocol: CAM01

Database Lock: yyyy-mm-dd

Table 14.3.3.2 Summary of Treatment-Emergent Adverse Events, by SOC and PT (Safety Analysis Set)

System Organ Class (SOC) Preferred Term (PT)	Part A:		Part B:		LMN-101 Overall (N=xxx) n (%) m	Placebo (N=xxx) n (%) m	Overall (N=xxx) n (%) m
	LMN-101 3000 mg (N=xxx) n (%) m	LMN-101 300 mg (N=xxx) n (%) m	LMN-101 1000 mg (N=xxx) n (%) m	LMN-101 3000 mg (N=xxx) n (%) m			
	Subjects with at least one TEAE	xx (xx.x%) xx	xx (xx.x%) xx	xx (xx.x%) xx			
SOC1	xx (xx.x%) xx	xx (xx.x%) xx	xx (xx.x%) xx	xx (xx.x%) xx	xx (xx.x%) xx	xx (xx.x%) xx	xx (xx.x%) xx
PT1	xx (xx.x%) xx	xx (xx.x%) xx	xx (xx.x%) xx	xx (xx.x%) xx	xx (xx.x%) xx	xx (xx.x%) xx	xx (xx.x%) xx
SOC2	xx (xx.x%) xx	xx (xx.x%) xx	xx (xx.x%) xx	xx (xx.x%) xx	xx (xx.x%) xx	xx (xx.x%) xx	xx (xx.x%) xx
PT1	xx (xx.x%) xx	xx (xx.x%) xx	xx (xx.x%) xx	xx (xx.x%) xx	xx (xx.x%) xx	xx (xx.x%) xx	xx (xx.x%) xx

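### Protocol 8.3 makes AE recording optional for clinically significant laboratory, blood-pressure and pulse changes, so a non-serious grade 3 change can be missing from the TEAE tables and may not count toward the two-subject pause rule

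*Protocol*

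**What the plan says.** Protocol 8.3 sets the recording rule: "Clinically significant changes in laboratory values, blood pressure, and pulse need not be reported as AEs since they will be captured in those data listings". It then gives two exceptions: "However, abnormal values that constitute an SAE or lead to discontinuation of administration of treatment must be reported and recorded as an AE". The same section grades intensity by CTCAE version 5.0 and separates severity from seriousness: "An AE of severe intensity may not be considered serious".

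Three other parts of the plan depend on what is recorded as an AE:

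- **Tables.** Protocol 7.17: "The incidence and number of all reported AEs and treatment-related AEs will be tabulated by treatment group". SAP 12.1: "AE summaries will be restricted to TEAEs only". The shell of SAP Table 14.3.3.1 has a row headed "One Grade 3 or Higher TEAE".
- **Pause rule.** Protocol 4.3 lists, among the criteria for pausing dosing, "if two or more subjects experience the same grade 3 or higher AE". It also lists "if any subject experiences a SAE deemed related to the study drug", any AESI, and a judgement criterion based on accumulating SAEs or AEs.
- **Causality.** Protocol 8.2 requires a relationship assessment for each AE. It asks for none on a laboratory or vital-sign value as such.

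Outside the AE route, Protocol 3.3 names clinically significant laboratory abnormalities and vital-sign changes as safety measures in their own right. SAP 12.3 provides laboratory summaries by visit, out-of-range counts, shift tables and abnormal-value listings. Laboratory clinical significance appears only in listings. SAP 12.4 provides for an assessment of the clinical significance of each vital-sign result and a summary of its interpretation at each scheduled visit.

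**The concern.** The exemption is not limited to trivial out-of-range values. It applies to changes already judged clinically significant. The only ones that must be recorded are those that meet the SAE definition or end dosing, and 8.3 itself accepts that a severe event need not be serious. That leaves a gap, chiefly a non-serious grade 3 value in a participant who continues dosing.

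This is a first-in-human study with safety and tolerability as the primary endpoint and dose escalation governed partly by a count of grade 3 AEs. If the exemption is used, three things depend on the investigator's choice to record: whether the change has a grade and causality assessment, whether it reaches the tables readers use to judge safety, and whether it clearly counts toward the pause rule. Two participants with the same result could be handled differently.

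**Working it through.** The plan states no operating characteristic to reproduce, so the check is mainly a comparison of texts.

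**1. Which changes fall in the gap.** Protocol 8.3 exempts laboratory values, blood pressure and pulse; temperature and respiratory rate are not named. Removing SAEs and treatment-stopping values leaves clinically significant, non-serious changes with dosing continued. Because severe and serious are distinct, grade 3 changes can be among them.

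**2. Effect on the tables.** Protocol 7.17 tabulates reported AEs, and SAP 12.1 summarises TEAEs only. A change not reported as an AE cannot enter the TEAE, drug-related or grade 3 rows. This follows directly.

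**3. Effect on the pause rule.** The 4.3 criterion counts subjects who experience the AE; it does not say the AE must have been recorded. The general AE definition in Protocol 8 could be read to include an unrecorded change. On that reading it counts; if the reviewers work from recorded AEs, it does not. The documents do not settle this.

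**4. Whether the listings replace the AE record.** Protocol 8.3 justifies the exemption by pointing to the listings. The SAP shells compare as follows:

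| Output | CTCAE grade | Relationship to drug | Clinical significance |
|---|---|---|---|
| AE listing 16.2.7.1 | yes | yes | not applicable |
| Laboratory listings 16.2.8.1.1 to 16.2.8.2.2 | no | no | yes |
| Vital signs listing 16.2.9.1 | no | no | no (High/Low flag, value and change) |

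The laboratory tables classify results as Low, Normal or High, so a marginal value and a grade 3 value fall in the same cell. Post-baseline unscheduled results are left out of the summaries (SAP 3.1 and 12.3).

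**5. Size in the table.** Inputs: 4 active participants per Part B cohort and 12 active in Part B overall (Protocol 4.1). Suppose 2 of the 4 in one cohort have the same non-serious grade 3 laboratory change and continue dosing.

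- Recorded: 2/4 = 50.0% for that dose; 2/12 = 16.7% for Part B LMN-101 overall.
- Exemption used: 0/4 and 0/12, both 0%.
- Pause-rule count: 2 if recorded; 2 or 0 if not, depending on how 4.3 is read.

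**6. How often two participants might be affected.** The per-participant rate p is an assumption; the documents give none. Part B review is blinded and 4.3 does not separate active from placebo, so a cohort supplies 6 participants:

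P(at least 2 of 6) = 1 − (1 − p)^6 − 6p(1 − p)^5

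- p = 0.05: 1 − 0.7351 − 0.2321 = 3.3%
- p = 0.10: 1 − 0.5314 − 0.3543 = 11.4%
- p = 0.25: 1 − 0.1780 − 0.3560 = 46.6%

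Counting only the 4 active participants gives 5.2% at p = 0.10 and 26.2% at p = 0.25. Since 4.3 sets no per-cohort limit, all 20 participants could be counted, which gives 26.4% at p = 0.05. These are chances that two participants have the change. They do not include the chance that it goes unrecorded, and so are not chances that the exemption alters a decision.

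**The case against.** The other side has several fair points.

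- **A parallel route exists by design.** Laboratory values and vital signs are evaluated in their own right (Protocol 3.3 and 7.17), so absence from a TEAE row is not absence from the safety evaluation. This stands as to visibility. It does not supply a grade or a causality assessment, and laboratory clinical significance is listed, not counted.
- **Other text pulls against the exemption.** Protocol 8 requires all AEs to be recorded, and 7.14 includes AEs found by laboratory testing in the analysis. Both apply only once a change is treated as an AE, and neither withdraws 8.3. They make practice harder to predict.
- **The SAE exception is broad.** Protocol 8.1 includes important medical events that may need intervention, so some grade 3 changes would have to be recorded. That narrows the gap but does not close it.
- **The pause-rule consequence is uncertain.** The 4.3 criteria are introduced as inclusions, safety data are reviewed before each escalation, and the triggers for related SAEs, AESIs and general safety concern remain. This is right, so the pause-rule point is one of ambiguity only. The judgement trigger is itself worded in terms of AEs and SAEs.
- **The numbers are illustrative.** This also stands. The contrast of 2/4 with 0/4 restates recorded against not recorded, and the probabilities rest on assumed rates. The conclusion does not depend on them.

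**Conclusion.** The concern holds. The effect on the tables is firm: where the exemption is used, a clinically significant, non-serious change that does not stop dosing is absent from the TEAE, drug-related and grade 3 rows and has no required causality assessment. With 4 active participants per cohort, two such changes move the grade 3 row between 50.0% and 0%. The effect on the pause rule is an ambiguity, not a demonstrated failure: the documents do not say whether an unrecorded change counts.

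The conclusion assumes only that such a change can occur and that an investigator may use the option 8.3 gives. The values remain in the listings and laboratory or vital-sign summaries and can be seen at cohort review, so this should be fixed as a cheap improvement and does not invalidate the study.

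**What to change.** Replace the exemption in Protocol 8.3 with a rule such as: *a laboratory, blood-pressure or pulse change that the Investigator considers clinically significant, and at minimum any such change of CTCAE v5.0 grade 3 or higher, is recorded as an AE with its grade and causality.* The grade 3 clause alone would settle the pause-rule count and the grade 3 row. The wider clause also brings lower-grade clinically significant changes into the TEAE and drug-related tables.

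Optionally, add one table under SAP 12.3 by treatment group: n (%) with any clinically significant laboratory abnormality, and worst post-baseline CTCAE grade, including unscheduled results. If dosing has already finished, this table can still repair the laboratory reporting, though not the missing causality assessments or the pause rule.

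The cost is a one-sentence amendment with HREC re-approval (Protocol 10), a few more AE records in 20 participants, and a little programming if the table is added.
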